7.5 Early Termination Visit

The Protocol Director should be notified within 48 hours if a participant terminates the study prior to completing all study visits.

If a participant discontinues the study early for any reason then the following assessments for the Early Termination Visit should occur:

- Concomitant medications
- Signs/Symptoms/Adverse Effects

However, if the participant discontinues the study between Year 1 and Year 2, the Day 28 visit of Year 1 can serve also as the Early Termination Visit.

7.6 Definition of Evaluations

7.6.1 Written Informed Consent

Participants will be given the IRB-approved informed consent form at the Screening/Entry Visit. A discussion of risks and possible benefits of participation in this study will be provided to the participants. Participants then will be asked for any questions and to read/sign the consent form. The consent form will be signed prior to the performance of any study procedures. A copy of the informed consent document will be given to the participant for her records. The rights and welfare of the participants will be protected by emphasizing to them that the quality of their medical care will not be adversely affected if they decline to participate in this study.

7.6.2 Eligibility Determination

At the completion of all protocol-defined screening procedures, the Eligibility Determination Form will be completed and signed by the Study Coordinator according to study criteria (see sections 4.1 and 4.2). Eligible participants giving informed consent will be enrolled in the study.

7.6.3 Demographics/Medical History/Pregnancy History

Participant demographics will include date of birth and race/ethnicity. A medical history will be obtained and must be recorded in the source documents. The medical history must include:

- All past medical diagnoses, acute or chronic
- Influenza Vaccination History within the past 5 years

A pregnancy history will be obtained and must be recorded in source documents. The pregnancy history must include:

- Expected delivery date (in order to calculate gestational age)
- Pre-pregnancy weight
- Number of prior pregnancies
- History of prior preterm births

7.6.4 Update Medical History/Review Eligibility Requirements

At the Day 0 visit of Year 2, the medical history from Year 1 will be updated. Additionally, eligibility criteria will be reviewed and only participants who still meet all Inclusion Criteria (other than the pregnancy criterion) and still meet no Exclusion Criteria will be entered into Year 2 of the study. Participants no longer eligible will be terminated from the study.

7.6.5 Concomitant Medications

At the Entry Visit record all current and past (within the last 28 days) prescription and non-prescription medications. At subsequent visits, record changes in medications since the last study visit. Additionally, record any vaccinations, allergy shots, or PPD tests received within the past 28 days.

7.6.6 Signs/Symptoms/Adverse Events

All Grade 2 or higher signs, symptoms, and toxicities and their relationship to study procedures must be documented in the participant's record.

Any sign or symptom that leads to discontinuation of study, regardless of grade, must be recorded on source documents.

Refer to the Common Terminology for Adverse Effects, Version 5.0, November 27, 2017, located at

https://ctep.cancer.gov/protocoldevelopment/electronic_applications/docs/CTCAE_v5_Quick_Reference_8.5x11.pdf

Report diagnoses for clinical events and other diseases and record whether they were related to study procedures.

7.6.7 Vital Signs and Weight

Assessment of vital signs will include measurement of resting blood pressure, pulse, respiratory rate, and temperature. Weight should be measured in kilograms.

7.6.8 Height

Height should be measured in centimeters.

7.6.9 Hemoglobin

If no clinical value for hemoglobin is available from clinical care within 8 weeks prior to entry, a hemoglobin will be assessed at the Screening/entry visit.

7.6.9 Phlebotomy

Phlebotomy will be performed at each visit using antiseptic technique. See Appendix 1: Blood Draw Requirements for blood draw instructions for each visit.

7.6.10 IIV4 Administration

Participants will be administered the seasonal IIV4 vaccine in the left or right deltoid muscle using antiseptic technique. Volunteers will be observed in clinic for 15 minutes after vaccination to monitor for any immediate serious reactions. The location of the injection, lot number and expiration date will be documented.

In Year 1 for participant convenience, the IIV4 may be given as part of participant's routine clinical care (i.e., outside of this research protocol) as part of participant's recommended obstetrical clinical care. In this case, the administration of the vaccine will be done on the same day following the Day 0 evaluations described in Section 7.1

In Year 2, all study related procedures, including the administration of the seasonal IIV4 vaccine will be completed by the Research Study Team as part of this study protocol.

8.1 Definitions of AEs, Adverse Reactions, and Serious Adverse

ADVERSE EVENTS AND TOXICITY MANAGEMENT

An adverse event (AE) is any untoward medical occurrence in a clinical study participant administered a pharmaceutical product, which does not necessarily have a causal relationship with the treatment. An AE can therefore be any unfavorable and/or unintended sign, symptom, or disease temporally associated with the use of a medicinal product, whether or not considered related to the medicinal product. AEs may also include pre-or post-treatment complications that occur as a result of protocol specified procedures, lack of efficacy, overdose, drug abuse/misuse reports, or occupational exposure. Preexisting events that increase in severity or change in nature during or as a

 Medical or surgical procedures such as surgery, endoscopy, tooth extraction, and transfusion. The condition that led to the procedure may be an adverse event and must be reported

consequence of participation in the clinical study will also be considered AEs. An AE

- Pre-existing diseases, conditions, or laboratory abnormalities present or detected before the Screening Visit that do not worsen
- Situations where an untoward medical occurrence has not occurred (e.g., hospitalization for elective surgery, social and/or convenience admissions)
- Overdose without clinical sequelae

does not include the following:

 Any medical condition or clinically significant laboratory abnormality with an onset date before the consent form is signed and not related to a protocol-associated procedure is not an AE. It is considered to be pre-existing and should be documented as medical history.

A serious adverse event (SAE) is defined as an event that results in the following:

Death

8

Events

- Life-threatening (note: The term "life-threatening" in the definition of "serious" refers to an event in which the participant was at risk of death at the time of the event; it does not refer to an event that hypothetically might have caused death if it were more severe.)
- In-patient hospitalization or prolongation of existing hospitalization
- Persistent or significant disability/incapacity
- A congenital anomaly/birth defect
- A medically important event or reaction; such events may not be immediately life-threatening or result in death or hospitalization but may jeopardize the participant or may require intervention to prevent one of the other outcomes constituting SAEs. Medical and scientific judgment must be exercised to determine whether such an event is reportable under expedited reporting rules. Examples of medically important events include intensive treatment in an emergency room or at home for allergic bronchospasm; blood dyscrasias or convulsions that do not result in hospitalization; and development of drug dependency or drug abuse. For the avoidance of doubt, infections resulting from contaminated medicinal product will be considered a medically important event and be subject to expedited reporting requirements.

Clinical laboratory abnormalities and other abnormal assessments without clinical significance are not recorded as AEs or SAEs. However, laboratory abnormalities that require medical or surgical intervention or lead to study drug discontinuation must be recorded as an AE, as well as an SAE, if applicable. In addition, laboratory or other abnormal assessments (e.g., electrocardiogram, x-rays, vital signs) that are associated with signs and/or symptoms must be recorded as an AE or SAE if they meet the definition of an AE or SAE as described above. If the laboratory abnormality is part of a syndrome, record the syndrome or diagnosis (e.g., anemia), not the laboratory result (i.e., decreased hemoglobin).

8.2 Assessment of Adverse Events and Serious Adverse Event

The Protocol Director is responsible for assessing AEs and SAEs for causality and severity, and for final review and confirmation of accuracy of event information and assessments.

The Protocol Director is responsible for assessing the relationship to study drug treatment using clinical judgment and the following considerations:

- No: Evidence exists that the adverse event has an etiology other than the study drug. For SAEs, an alternative causality must be provided (e.g., pre-existing condition, underlying disease, intercurrent illness, or concomitant medication).
- Yes: There is reasonable possibility that the event may have been caused by the investigational medicinal product.

Ineffective treatment should not be considered as causally related in the context of adverse event reporting. The relationship to study procedures (e.g., invasive procedures such as venipuncture or biopsy) should be assessed using the following considerations:

- No: Evidence exists that the adverse event has an etiology other than the study procedure.
- Yes: The adverse event occurred as a result of protocol procedures (e.g., venipuncture).

The severity grading of AEs will be assessed as Grade 1, 2, 3, or 4 using the Common Terminology for Adverse Effects, Version 5.0, November 27, 2017, located at https://ctep.cancer.gov/protocoldevelopment/electronic applications/docs/CTCAE v5 Quick Reference 8.5x11.pdf and Grade 2 or higher AEs recorded.

For AEs associated with laboratory abnormalities, the event should be graded on the basis of the clinical severity in the context of the underlying conditions; this may or may not be in agreement with the grading of the laboratory abnormality.

8.3 Instructions for Reporting Adverse Events and Serious Adverse Events

SAEs, regardless of cause or relationship, that occur after the participant first consents to participate in the study (i.e., signing the informed consent) and throughout the duration of the study, including the protocol-required post treatment follow-up period, must be reported on the CRF. This also includes any SAEs resulting from protocol-associated procedures performed from screening onwards. All AEs, regardless of cause or relationship, that occur from initiation of study drug until 4 weeks after last administration of study drug must be reported on the CRF. Any SAEs and deaths that occur after the Post-Treatment follow-up visit OR within 30 days of the last dose of study drug (whichever is longer), regardless of causality, should also be reported. All AEs should be followed up until resolution or until the adverse event is stable, if possible. Investigators are not obligated to actively seek SAEs after the 30-day period.

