6 STUDY INTERVENTION/INVESTIGATIONAL PRODUCT

6.1 Study Product Description

6.1.1 Acquisition

The study product will be shipped from the manufacturer to the investigational pharmacy at the study site. IIV4 will be supplied by Glaxosmithkline Biologicals as Fluarix® Quadrivalent.

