7 STUDY SCHEDULE

7.1 Schedule of Events

Fuelvetion	Year 1		Year 2		Early Termination			
Evaluation	D0	D7	D28	D0	D7	D28	Visit	
Written Informed Consent	Х							
Eligibility Determination	Х							
Demographics/Medical History/Pregnancy History	Х							
Update Medical Hx/ Review Eligibility Requirements				Х				
Concomitant Medications	Х	Х	Х	Х	Х	Х	X	
Signs/Symptoms/Adverse Events	Х	Х	Х	Х	Х	Х	X	
Vital Signs/Weight	Х	If clinically	y indicated	Х	If clin indic			
Height	Х							
Hemoglobin*	Х							
Phlebotomy	Х	Х	Х	Х	Х	Х		
IIV4 Administration	Χ [†]			X				

^{*} An adequate hemoglobin level (i.e., >9.0g/dL) from within 8 weeks of entry can substitute for the research hemoglobin draw); † - IIV in Year 1 may be administered by clinic staff at Stanford Ob/Gyn Flu Clinic as part of participant's routine care (i.e., outside of research study)

7.2 Year 1, Day 0

The following will be performed at screening (see Section 7.6 for a detailed explanation of each evaluation)

- Written Informed Consent
- Eligibility Determination
- Demographics/Medical History/Pregnancy History
- Concomitant Medications
- Signs/Symptoms/Adverse Events
- Vital Signs/Weight
- Height
- Hemoglobin
- Phlebotomy
- IIV4 Administration (may be administered by clinic staff at Stanford's Ob/Gyn Clinic as part of participant's recommended obstetrical clinical care)

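### Does a Year 1 vaccine dose given by the clinic fall outside adverse event reporting, so that events in pregnancy are lost?

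*Protocol*

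**What the plan says.** Section 8.3 sets the CRF duty for non-serious events: "All AEs, regardless of cause or relationship, that occur from initiation of study drug until 4 weeks after last administration of study drug". The protocol does not define study drug. Serious events are handled separately in the same section and are reportable from consent.

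Section 7.6.10 allows the Year 1 vaccine, for the participant's convenience, to be given as "routine clinical care (i.e., outside of this research protocol)", on the same day and after the Day 0 evaluations. The footnote to the schedule in Section 7.1 describes it as "routine care (i.e., outside of research study)". For the second season the wording differs: "In Year 2, all study related procedures, including the administration of the seasonal IIV4 vaccine will be completed by the Research Study Team". Section 6.1.1 says of supply: "The study product will be shipped from the manufacturer to the investigational pharmacy at the study site".

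On causality, Section 8.2 makes the Protocol Director responsible for "assessing the relationship to study drug treatment using clinical judgment" and, separately, for the relationship to study procedures. Section 7.6.6 covers signs, symptoms and toxicities of Grade 2 or higher and says that "their relationship to study procedures must be documented". On severity, Section 8.2 has "Grade 2 or higher AEs recorded".

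The secondary endpoint in Section 2, reported under Section 10.3, is adverse events of Grade 2 or higher.

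**The concern.** Section 8.3 is the only place that expressly says which non-serious events must go on the CRF, and its clock starts at study drug. If a dose given outside the research is not study drug, the clock for a woman vaccinated by the clinic starts at Year 2 Day 0. If she is not entered into Year 2, because she is pregnant again (Section 4) or no longer eligible (Section 7.6.4), it never starts. The contrast that Section 7.6.10 draws with Year 2, and the description of study product as stock held by the investigational pharmacy, both lend this reading some support.

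What would be at stake is the only secondary endpoint, in the season that is the subject of the trial. A loss could run in one direction only: it would lower the Year 1 (pregnant) figure and leave Year 2 intact, because every Year 2 dose is given by the study team. A later analysis plan can choose among collected events but cannot recover events that were never collected.

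**Working it through.** The protocol states no figure on this point, so there is none to reproduce. The check compares the reporting windows under two readings and then asks whether the endpoint data depend on the choice.

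**Inputs.** Participation lasts about 56 weeks (Section 1). The last visit is 4 weeks after the Year 2 dose, so Year 2 Day 0 falls at about week 56 − 4 = 52. The Section 8.3 window runs from the first study drug to 4 weeks after the last.

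**Reading A: a clinic-given dose is not study drug.**

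| Year 1 dose given by | Year 2 dose | Section 8.3 window | Days covered of the 28 after the Year 1 dose |
|---|---|---|---|
| Study team | Yes | 52 + 4 = 56 weeks | 28 |
| Study team | No | 4 weeks | 28 |
| Clinic | Yes | weeks 52 to 56 = 4 weeks | 0 |
| Clinic | No | 0 weeks | 0 |

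**Reading B: IIV4 is study drug whoever gives it.** The window opens at Year 1 Day 0 for every woman, and all 28 days are covered in every row.

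**Which reading fits the document.** Section 1 describes immunization with IIV4 in both years as the intervention, and Section 4 does the same. IIV4 administration is a scheduled Year 1 Day 0 item in Section 7.1, with a footnote only on who may give it. Section 7.4 times the Day 7 and Day 28 visits from the vaccine administration in both years without distinguishing the giver. Section 6.1.1 concerns supply and defines nothing. Reading A would leave the pregnant season of a trial about vaccination in pregnancy with no study drug for some of its participants. Reading B is the natural one.

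**Whether the endpoint depends on the reading.** Three links lead from event to endpoint, and none uses the term study drug:

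1. Assessment: Sections 4, 7.1 and 7.4 have adverse events assessed at every visit, including Year 1 Day 7 and Day 28, for every woman.
2. Documentation: Section 7.6.6 requires all events of Grade 2 or higher in the participant's record, and Section 8.2 has them recorded.
3. Database: Section 13.2 has clinical data entered from source documents or data collection forms, and Section 13 requires entries to agree with their source.

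Sections 2 and 10.3 count events of Grade 2 or higher, with no condition on causality. The endpoint therefore draws on data that the protocol requires under either reading.

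**Upper bound if everything failed.** Let u be the share of women vaccinated by the clinic. Suppose Reading A is applied, nothing documented reaches the CRF, and event frequency is equal in both groups. Then counted/true = 1 − u for women with non-serious events of Grade 2 or higher. With u assumed at 0.2, 0.5 and 0.8 the ratio is 0.8, 0.5 and 0.2, so an assumed 10 true cases among 50 women would be counted as 8, 5 or 2. Both u and the 10 cases are assumptions; Section 7.6.10 sets no limit on u. The figures show the worst case of a chain that Sections 7.6.6, 8.2 and 13.2 break. They do not estimate a bias.

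**The case for a change.** The strongest case for a change is that documentation in a participant record is not the same as a CRF duty. Section 13.2 does not say which adverse events are entered, and only Section 8.3 names the CRF for non-serious events. A coordinator who takes the phrase about being outside the protocol at face value could leave Year 1 events after a clinic dose in the chart. On that reading nothing requires those events to be rated against the vaccine either: Section 7.6.6 asks only about study procedures, and Section 8.2 refers to study drug. The repair would cost a few words and one CRF field.

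Part of this stands. The term is undefined, and on a strict reading Section 8.3 does not expressly reach the clinic-given dose. The same sentence in Section 8.3 asks for events of any grade while Sections 7.6.6 and 8.2 record Grade 2 or higher, which is a separate slip.

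Neither point reaches a result. Section 8.3 sets a minimum duty and bars nothing outside its window, so it is silent on one case and does not contradict Section 7. The study has one site and one Protocol Director, so readings are unlikely to diverge, and events documented under Section 7.6.6 remain in the record to be entered. The causality rating does not enter the endpoint, and Section 8.4.1 already sorts serious events by relation to the vaccine, which suggests that IIV4 is what Section 8 means by study drug. The difference over grades concerns Grade 1 events only and leaves the count of Grade 2 or higher unchanged.

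**Conclusion.** The wording mismatch between Sections 8.3 and 7.6.10 is real, but no loss to the secondary endpoint is shown and no change to the plan is called for. On the natural reading, that IIV4 is the study intervention in both years, all 28 days after the Year 1 dose are covered for every woman and the effect is zero. On the strict reading the Section 8.3 window misses those days for women vaccinated by the clinic, yet events of Grade 2 or higher must still be assessed at Day 7 and Day 28 and documented, and they can be entered from source. Serious events are unaffected under either reading.

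The conclusion assumes that the site follows Sections 7.4 and 7.6.6 and enters what it documents, as Section 13.2 describes. It would change only if the site were found to be leaving documented Year 1 events out of the database. Defining study drug as IIV4 whoever gives it, and aligning the grade threshold in Section 8.3 with Sections 7.6.6 and 8.2, would be reasonable housekeeping at a future amendment. Neither would alter an analysis.

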8.4 Reporting Procedures

8.4.1 Regulatory Reporting for Studies Not Conducted Under an IND

For those events meeting the previously described definition of Serious Adverse Events, the completion of an SAE report form is required. For SAEs related to vaccine, a VAERS form will be filled out and submitted to the Vaccine Adverse Event Reporting System (VAERS) per federal regulations. The VAERS form will simultaneously be sent to the sponsor. SAEs and events that meet the Prompt Reporting guidelines (events meeting the criteria for Unanticipated Problems) will also be reported to the Stanford IRB as required. Unexpected deaths or life-threatening experiences related to the research will be reported to the sponsor and to the IRB within 5 working days from when the investigator learns of event. SAEs not related to vaccine will be reported to the IRB on an annual basis.

8.5 Safety Oversight

The Clinical Core Principal Investigator will oversee compliance with the protocol, the participant's safety and any unanticipated problems involving risks to participants and will report these events as described above. Unanticipated problems and serious adverse events will be reported to the Stanford IRB as required.

3 3 7 = 1 1

9 CRITERIA FOR STUDY DISCONTINUATION

9.1 Criteria for Permanent Study Discontinuation

- Requirement for prohibited concomitant medications (such as immunosuppressant medication)
- Pregnancy during Year 2 of Study
- Participant no longer meeting eligibility requirement at Day 0 visit of Year 2 (other than pregnancy requirement)
- Clinical reasons such that continued participation in the study may be detrimental to the participant's health as judged by the Protocol Director
- Failure by the participant without reasonable cause to attend study visits
- Request by the participant to withdraw.
- Request of the primary care provider if s/he thinks the study is no longer in the best interest of the participant.
- Participant judged by the investigator to be at significant risk of failing to comply with the provisions of the protocol as to cause harm to self or seriously interfere with the validity of the study results.
- Participant died.
- At the discretion of the IRB or Study Investigators.

Starriora 6 to 661 ii. Respense to ilimaoriza vaccine Barring Programoy. Vilo_1000p2021

10 STATISTICAL CONSIDERATIONS

10.1 Study Hypotheses

We hypothesize that exposure to influenza vaccination will result in immunity to influenza in the majority of study participants and will be well-tolerated forming the basis of novel immunologic insights.

